## **6. Plan for reporting UPIRSOs (including Adverse Events) to the IRB**

The principal investigator will report the following types of events to the IRB:

Any incident, experience or outcome that meets ALL 3 of the following criteria:

1. Is unexpected (in terms of nature, specificity, severity, or frequency) given (a) the research procedures described in the protocol-related documents, such as the IRB-approved protocol and informed consent document and (b) the characteristics of the subject population being studied; AND
2. Is related or possibly related to participation in the research (*possibly related* means there is a reasonable possibility that the incident, experience, or outcome may have been caused by the procedures involved in the research); AND
3. Suggests that the research places subjects or others at greater risk of harm (including physical, psychological, economic, legal, or social harm) than was previously known or recognized.

Unanticipated Problems Involving Risks to Subjects or Others (UPIRSOs) may be medical or non-medical in nature, and include – but are not limited to – *serious, unexpected, and related adverse events* and *unanticipated adverse device effects*. **Please note** that adverse events are reportable to the IRB as UPIRSOs **only** if they meet all 3 criteria listed above.

These UPIRSOs/SAEs will be reported to the IRB in accordance with IRB Policy 710, using the appropriate forms found on the website. All related events involving risk but not meeting the *prompt* reporting requirements described in IRB Policy 710 should be reported to the IRB in summary form at the time of continuing review. If appropriate, such summary may be a simple brief statement that events have occurred at the expected frequency and level of severity as previously documented. In lieu of a summary of external events, a current DSMB report can be submitted for research studies that are subject to oversight by a DSMB (or other monitoring entity that is monitoring the study on behalf of an industry sponsor).

## **7. Plan for reporting adverse events to co-investigators on the study, as appropriate the protocol’s research monitor(s), e.g., industrial sponsor, Yale Cancer Center Data and Safety Monitoring Committee (DSMC), Protocol Review Committee (PRC), DSMBs, study sponsors, funding and regulatory agencies, and regulatory and decision-making bodies.**

For the current study, the following individuals, funding, and/or regulatory agencies will be notified (choose those that apply):

- All Co-Investigators listed on the protocol.
- Yale Cancer Center Data and Safety Monitoring Committee (DSMC)
- National Institutes of Health

- Food and Drug Administration (Physician-Sponsored IND # \_\_\_\_\_)
- Medical Research Foundation (Grant \_\_\_\_\_)
- Study Sponsor
- Other Data Safety Monitoring Board (DSMB) or Committee (DSMC)

The principal investigator [name], will conduct a review of all adverse events upon completion of every study subject. The principal investigator will evaluate the frequency and severity of the adverse events and determine if modifications to the protocol or consent form are required.

- d. For multi-site studies for which the Yale PI serves as the lead investigator: **N/A**
  - i. How will adverse events and unanticipated problems involving risks to subjects or others be reported, reviewed and managed?
  - ii. What provisions are in place for management of interim results?
  - iii. What will the multi-site process be for protocol modifications?

12. **Statistical Considerations:** Describe the statistical analyses that support the study design.

Main outcomes are prolonged smoking abstinence (Y/N at each point) and rates of 7-day point prevalence of abstinence(Y/N at each point). Following the recommendations of the Society for Research on Nicotine and Tobacco workgroup, the 7-day point prevalence is defined by self-reported smoking abstinence for the last 7 days, and expired carbon monoxide <10 ppm. Prolonged smoking abstinence is self-reported smoking abstinence starting with a 2-week grace period after the quit day (i.e., last 5 weeks of the treatment phase) without relapse to: the end of the trial, 1 month and 3 months post trial. Relapse is defined by a) smoked for 7 consecutive days or b) smoked at least once each week for 2 consecutive weeks, or c) missed 2 consecutive weekly appointments or 2) failed breath test at any previous outcome assessment. Additional outcomes include measures of withdrawal (MNWS and QSU-B), and response inhibition (Stroop and SST).

Data Analysis: We will follow CONSORT guidelines for the conduct and reporting of the trial. Descriptive statistics will be used to summarize the data on all randomized subjects, although, as per CONSORT, these parameters will not be included in the statistical model for primary analyses. Aim #1: To determine whether progesterone with TNP is superior to placebo and TNP we will use generalized estimating equations (GEE), an autoregressive correlation structure a binomial distribution and either identity or log link. A time-by-treatment interaction will be included in the GEE model. The 8-week period will include a continuous version for the time variable and the follow up periods will treat time as categorical. A GEE model such as this can evaluate whether there is an overall difference between the progesterone and the placebo groups and whether the rate of change in smoking abstinence is different between the two groups. For data that are missing, we will perform inverse weighting to determine if data are missing at random (25). The weight will be the inverse of the probability not dropping out. If there are concerns of informative dropout and/or informative intermittent missing data, which is typical of clinical trial data, we will use

pattern mixture models (26) and perform sensitivity analyses. In sensitivity analyses, participants who miss visits will be coded as smoking. Exploratory analysis will include plasma estradiol and progesterone levels as covariates in order to determine if they contribute to treatment response and PANAS scores as mediators of response to progesterone or placebo. Secondary analyses (the MNWS QSU-B) will be modelled similarly. The main outcome measures for the Stroop test are throughput and interference score. For the SST, the main outcomes are stop signal reaction time (msec) and go reaction time (msec). We will use hierarchical linear models with each cognitive measure as separate longitudinal outcomes and treatment group assignment as regressors.

**Power:** The sample size of 25 per condition was selected to provide an adequate assessment of feasibility and estimate effect sizes. Nonetheless, we determined what level of power we would have based upon a significance level of  $p < 0.05$ , 2 sided test for 7-day or prolonged abstinence. If rates of abstinence are 0.2 in the TNP only group and 0.4 in the progesterone and TNP group then the power would be 88%. If the rate of abstinence in the treated group is 0.38, power is reduced to 80%. In prior studies with the Stroop and SST, we found effect sizes  $> 0.5$  of progesterone vs placebo. Our sample size would have adequate power ( $> 80\%$ ) to detect a 2-fold difference in response. Clearly, these are large differences between groups but would provide a stable effect size estimate for a larger trial if findings are suggestive of a therapeutic effect of the combination treatment.

**Timeline:** We will use the first 3 months for study set up that will include final human subjects' approval, hiring and training of staff, database set up, computerization of the interview and assessment measures. Recruitment will begin immediately afterward. We will conduct ongoing data cleaning and will prepare reports for the human subjects' board, the DSMB and NCI at regular intervals. The final analysis and study report will occur in the last 3 months of the work period.

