#### *Human subjects*

**Recruitment:** Recruitment will take place over 1.5 years, requiring enrollment of approximately 2-3 subjects per month. In our previous studies, we have been able to recruit on average 4 female smokers per month. Recruitment is further explained in Human Subjects but will be accomplished by direct screening in our reproductive health centers (20% of women seen for services in these centers are smokers), direct mail invitations, posters and flyers placed in local obstetrician-gynecologist offices. We have successfully used these techniques to recruit substance users, smokers and women with premenstrual dysphoric disorder in prior clinical trials. [name] has a secondary appointment in Obstetrics & Gynecology and has conducted numerous studies that entailed screening women in the reproductive health settings of Yale New Haven Hospital and their faculty (see Biosketch).

Update June 2017: All participants had blood levels of progesterone drawn. We were blind to assignment of participants but at the end of the study found that those who were randomized to active progesterone had low progesterone levels. This could be due to the progesterone preparation or the fact that smokers metabolize it very quickly. In any case, the low progesterone levels in the active treatment group obviates our ability to test our hypothesis that progesterone augmentation assists abstinence for smokers. Given the lack of funds, we cannot repeat the project. Rather, we are recruiting a second cohort and are using a commercially available oral micronized progesterone rather than the previous medication that was compounded for the study. We plan to enroll a minimum of 12 people with an imbalanced ratio of 6 active to 1 placebo. We will continue to obtain plasma levels of progesterone. This will enhance our ability to test our hypothesis. If need be in a final analysis, and give that this is a pilot project, we may be able to use the participants randomized to placebo in the first cohort and second cohort and the participants randomized to active in the second cohort.

Update September 2017: We request an additional blood draw (timeline is around Visit #6 or #7 to confirm progesterone plasma levels and compliance with pill taking. The second blood draw will be the same as the first one, completed at a professional lab on the first floor of the research site building. Approximately 6 ccs of blood will be drawn for each.

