Urn Randomization: To increase the likelihood that the two groups are balanced for age and the amount of smoking, participants will be assigned to the two study conditions through “urn” randomization (Stout *et al*, 1994). A categorical variable will be created based on the number of cigarettes/day in the month before randomization: 1= $<15$ ; and 2= $\geq 15$  or more cigarettes on average, per day, to distribute severity of smoking evenly over the two groups.

Update June 2017: We plan to enroll a minimum of 12 people with an imbalanced ratio of 6 active to 1 placebo.

We will post the study on the research team’s website [www.ResearchForHer.com](http://www.ResearchForHer.com), YCCI’s Help Us Discover database, and on Yale’s Department of Psychiatry Website as well as other websites. We will also include the study in some of Yale’s online newsletters.

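### The smoking-level factor that drives the urn allocation is not among the primary GEE terms; adding it is cheap and gains little in the randomised comparison, and if it is added the identity link should be avoided.

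*Combined protocol and SAP*

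**What the plan says.** **Allocation.** Under Human subjects, the Urn Randomization paragraph aims to balance the arms on age and amount of smoking. Only smoking is then defined: "A categorical variable will be created based on the number of cigarettes/day in the month before randomization", cut at 15 per day, "to distribute severity of smoking evenly over the two groups". No age category is given.

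**Primary model.** In Section V, item 12 (Data Analysis), all randomised women are described at baseline, but "as per CONSORT, these parameters will not be included in the statistical model for primary analyses". Aim #1 uses GEE with an autoregressive correlation, "a binomial distribution and either identity or log link". On terms, "A time-by-treatment interaction will be included in the GEE model". There is no rule for choosing between the two links and none for a model that does not converge.

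**Sample size.** Under Power: "The sample size of 25 per condition was selected to provide an adequate assessment of feasibility and estimate effect sizes".

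**Second cohort.** The June 2017 update (Recruitment, repeated in Section VI.A, item 2) reports that the team "at the end of the study found that those who were randomized to active progesterone had low progesterone levels". It adds at least 12 women at 6 active to 1 placebo. It then says "If need be in a final analysis, and give that this is a pilot project, we may be able to" set second-cohort active women against placebo women of both cohorts.

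**The concern.** A variable used to restrict the randomisation normally appears in the primary model. If it predicts outcome, balancing on it and then ignoring it makes the standard error slightly too large, and some precision that the design has already paid for is lost. Here the factor is binary, recorded before randomisation and costs one parameter, and the plan does not say that leaving it out is deliberate.

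Two practical matters follow. With 50 women, adding a covariate to a binomial model makes the choice of link matter, and the plan leaves that choice open. Also, the pooled comparison in the June 2017 update is not protected by the urn, so smoking level could act there as a confounder and not merely as a precision variable.

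**Working it through.** **Inputs from the documents:** 25 per arm, two-sided 0.05, abstinence 0.20 vs 0.40, cut at 15 cigarettes/day, second cohort of at least 12 at 6:1. **Assumptions, not in the documents:** half the women in each smoking stratum, the stratum abstinence rates, the within-woman correlation, no dropout, and 25 first-cohort placebo women.

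**1. The plan's own power figure.** For 0.20 vs 0.40, the null SE is √(2×0.30×0.70/25) = 0.1296 and the alternative SE is √((0.16+0.24)/25) = 0.1265. Power = Φ((0.20 − 1.96×0.1296)/0.1265) = 33.5%. For 0.38 it is 28.5%. The stated 88% and 80% are not reproduced at 25 per arm; they appear at 100 per arm (87.6%, 80.6%). That is a separate matter, but it means the gain below should be read from a base in the 30s or low 40s, not 88%.

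**2. Gain from the factor, single endpoint.** Power = Φ(0.20/SE − 1.96), with SE = 0.1265×√(1 − f), where f is the share of outcome variance that the factor removes.

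| Odds ratio of factor | f | SE | Power |
|---|---|---|---|
| 1 | 0% | 0.1265 | 35.2% |
| 2 | 2.4% | 0.1250 | 36.0% |
| 4 | 9.0% | 0.1207 | 38.1% |

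**3. Gain in the repeated-visit model.** 5,000 simulated trials per scenario: 8 weekly visits at constant rates, urn within stratum, logistic GEE with AR(1), standardised week-8 risk difference, Mancl–DeRouen SE. Monte Carlo error is about 0.7 points on power and 0.3 on type I error.

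| Control abstinence by stratum | Power without → with factor, corr. 0.8 | Same, corr. 0.5 |
|---|---|---|
| 20% / 20% | 35.2 → 34.6 | 40.9 → 40.4 |
| 25% / 15% (OR 0.53) | 33.2 → 33.1 | 40.0 → 39.8 |
| 30% / 10% (OR 0.26) | 32.5 → 33.4 | 41.3 → 43.0 |
| 35% / 5% (OR 0.10) | 33.5 → 37.0 | 39.3 → 45.4 |

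Type I error was 3.4–5.0% without the factor and 4.2–5.0% with it. With the ordinary robust SE, the adjusted test rejected 5.3–6.6% of the time under no effect.

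**4. The link.** Percentage of fits that failed or reached the boundary once the factor was added (ranges cover correlations 0.5 and 0.8):

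| Stratum rates | Identity, no effect | Identity, +20 points |
|---|---|---|
| 20/20 | 7–14 | 2–8 |
| 25/15 | 12–16 | 6–9 |
| 30/10 | 25–29 | 14–15 |
| 35/5 | 38–53 | 24–34 |

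Without the factor, identity failed in 1–2% under no effect. With it, the log link failed in at most 0.3%, except 5.4% at 35/5 with correlation 0.8; the logistic link failed in 0–0.3%, except 5.8% in the same scenario. A smaller independent simulation (200–300 trials per scenario, odds ratios 1 to 4, flat rates) gave identity 0–2% without and 4–28% with the factor, log 0–1.3%, logistic 0–0.3%. With abstinence declining over the weeks, log failed in 1.5% (OR 2) and 7.5% (OR 4).

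The mechanism is sparse cells. With 12.5 women per arm-by-stratum cell and no effect, P(at least one cell has no abstainer) = 1 − (1−(1−a)^12.5)²(1−(1−b)^12.5)², where a and b are the stratum rates. This is 0.22, 0.29, 0.48 and 0.78 for the four rows.

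**5. Pooled comparison.** Twelve women at 6:1 is about 10 active and 2 placebo, so 10 active vs 25+2 = 27 placebo. By exact binomial with a 50% share of heavier smokers, P(gap in smoking level >20 points) is 28% for 10 vs 27, 19% for 18 vs 28 (21 women) and 15% for 24 vs 29 (28 women), against about 2% under the urn with 50 women. With an assumed 60% vs 30% share of heavier smokers and no effect, the unadjusted identity estimate was biased by about 0.04 (OR 2) to 0.07 (OR 4); adjustment roughly halved this. All active women are second-cohort but only 2/27 of the controls are, so 1 − 2/27 = 25/27 = 93% of any other cohort difference in abstinence stays in the estimate (10 points leaves 9.3).

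**The case against.** The strongest reply is that nothing is broken in the randomised comparison. An unadjusted primary analysis, declared in advance, is a legitimate choice in a pilot sized for feasibility; type I error is held; and the gain is about zero unless smoking level is strongly prognostic. All of that stands, and it is why the point is minor. It does not explain why the allocation factor alone should be left out when including it costs so little.

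A reader might infer that the factor cannot enter the model as written, or that a logistic link is required. The documents do not support this: the log link is already allowed and failed about as rarely as the logistic one. The identity-link failures also arise only once the factor is added, vary with assumed prognostic strength, and are less frequent at the planned effect than under no effect. They are not a defect of the plan as it stands.

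A reader might also infer that the plan bars the urn variable by name. It does not; the omission follows from the listed terms and the general exclusion of summarised parameters.

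On the pooled set, it is fair to say that non-concurrent controls are the larger problem and that the comparison is only conditional. Both are true; the smoking imbalance is an additional weakness that can be reduced.

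Finally, the simulations use eight weekly visits at mostly constant rates, whereas the quit date falls after the first week of treatment. The decimals should not be read as specific to this trial.

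**Conclusion.** The concern holds as a minor refinement. The urn factor is not among the primary model terms. The unadjusted 1:1 test is valid and at most slightly conservative, so no claim of invalidity is warranted. Adding the factor moves power from about −0.5 points (not prognostic) to about +6 points (very strongly prognostic), and the documents do not say where this trial lies.

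If the factor is added, the identity link is a poor choice: about 2–53% of simulated fits failed or reached the boundary across the assumed rates, correlations and effects, against about 0–2% without it. Log and logistic links are both workable. The direction is secure; the exact rates depend on the assumptions and on how failure is defined.

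In the pooled comparison, smoking level has a stronger claim to inclusion, with a 15–28% chance of a gap above 20 points on the assumed numbers. It would be wrong to infer that adjustment restores a randomised comparison.

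**What to change.** In Section V, item 12:

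- Add the urn variable (<15 vs ≥15 cigarettes/day) to treatment, time and treatment-by-time in the primary GEE, and keep the model without it as a sensitivity analysis.
- Name the log link. A logistic link with a standardised risk difference is an equally workable option. Do not use the identity link with this term.
- State a non-convergence rule in advance, including what is done if an arm or stratum has no abstinent woman, and use a small-sample-corrected robust standard error.
- Settle age: the Urn Randomization paragraph names it without a category. If age was used in the urn, include it as well.
- Date the change, record what was known by then (first-cohort progesterone levels by arm, by June 2017), and report both versions.
- If the pooled comparison is run, include smoking level, label the comparison non-randomised and mostly non-concurrent, and state that other cohort differences remain. A cohort term can only be a sensitivity analysis: at 20% abstinence the SE rises from √(0.16×(1/10+1/27)) = 0.148 to √(0.16×(1/10+1/2)) = 0.310.

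**Cost:** one parameter, already recorded before randomisation; about 0.5 points of power if smoking level is not prognostic; and a late amendment that must be disclosed as such. In the logistic simulations, the corrected standard error lowered nominal power by about 4 points in the adjusted model and about 3 in the unadjusted one; in return, type I error stayed at or below 5.0%.

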This study seeks to determine if modifying the hormonal milieu of the menstrual cycle, through administration of exogenous progesterone, will improve the effectiveness of treatments for smoking cessation in women. Progesterone, a gonadal hormone, is used clinically for treatment of endometrial hyperplasia, amenorrhea, dysfunctional uterine bleeding, and for assisted reproduction in women. Progesterone also shows promise for the treatment of multiple central nervous system disorders including cocaine addiction, seizure disorder, and traumatic brain injury (1, 2). The utility of progesterone for smoking cessation is suggested by a number of previous studies. In a clinical trial, progesterone dominance during the luteal phase of the menstrual cycle, as compared to estrogen dominance in the follicular phase, significantly enhanced smoking abstinence in women attempting to quit smoking (3). Our group conducted pioneering human studies to determine the safety and potential efficacy of progesterone for the treatment of nicotine addiction. In these studies, progesterone, compared to placebo, attenuated the pleasurable effects of cigarette smoking or intravenously administered nicotine in abstinent smokers (4, 5). Progesterone also reduced craving for cigarettes and improved response inhibitory function in abstinent female smokers (6). These findings are promising because attenuating nicotine reward, and improving withdrawal symptoms and response inhibition are potential treatment targets for nicotine addiction (7, 8). As the next step, we seek to determine if progesterone augments standard smoking cessation treatments (e.g., NRT) in regularly cycling women. We hypothesize that co-treatment with progesterone, compared to placebo, will enhance the effectiveness NRT for smoking cessation. To test this hypothesis, we propose an 8-week, double-blind, placebo-controlled clinical trial, which will randomize 50 smokers using a 1:1 assignment ratio to 400 mg/day progesterone or placebo. Consistent with the Clinical Practice Guidelines (9), all participants will also receive transdermal nicotine patch (TNP) plus brief counseling for smoking cessation during the study participation. The dose of TNP will be 21mg/24 hours for 4 weeks, 14mg for weeks 5 and 6 and 7 mg for weeks 7 and 8 for women who smoked at least 10 cigarettes per week. We will start a 14 mg/day dose of TNP for women who smoke less than 10 cigarettes per week.

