  - iv. The investigation will be conducted in compliance with the requirements for institutional (HIC) review and with the requirements for informed consent of the FDA regulations (21 CFR Part 50 and 21 CFR Part 56). X Yes  No
  - v. The investigation will be conducted in compliance with the requirements regarding promotion and charging for investigational drugs. X Yes  No
2. **Background Information:** Provide a description of previous human use, known risks, and data addressing dosage(s), interval(s), route(s) of administration, and any other factors that might influence risks. If this is the first time this drug is being administered to humans, include relevant data on animal models.

1) Progesterone: Progesterone, a natural hormone, is safe and well-tolerated by women. The safety, tolerability and efficacy of micronized progesterone is well established and it is FDA approved for hormone replacement therapy (HRT), absence of menstrual periods (amenorrhea), endometriosis, infertility treatment and preterm delivery. The recommended dose of progesterone for hormone replacement treatment is 200 to 400 mg/day, given as a single evening dose. After oral administration, micronized progesterone reaches its peak plasma levels in two to three hours and has an elimination half-life of three to four hours (18). Because of its short half-life progesterone will be given twice daily to maintain stable plasma levels. Progesterone doses higher than 400 mg/day will not be used since they are more likely to cause sedation. The safety and tolerability of micronized progesterone are well established.

Update June 2017: All participants had blood levels of progesterone drawn. We were blind to assignment of participants but at the end of the study found that those who were randomized to active progesterone had low progesterone levels. This could be due to the progesterone preparation or the fact that smokers metabolize it very quickly. In any case, the low progesterone levels in the active treatment group obviates our ability to test our hypothesis that progesterone augmentation assists abstinence for smokers. Given the lack of funds, we cannot repeat the project. Rather, we are recruiting a second cohort and are using a commercially available oral micronized progesterone rather than the previous medication that was compounded for the study. We plan to enroll a minimum of 12 people with an imbalanced ratio of 6 active to 1 placebo.

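### Allocation moved from 1:1 to 6:1 between cohorts, but the Aim 1 GEE has no cohort term and no stated analysis set, so pooling both cohorts carries part of any cohort difference into the treatment effect

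*Combined protocol and SAP*

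**What the plan says.** The Statement of Purpose (Section V, item 1) describes a trial that "will randomize 50 smokers using a 1:1 assignment ratio". The Power paragraph (Section V, item 12) matches it: "The sample size of 25 per condition was selected to provide an adequate assessment of feasibility and estimate effect sizes".

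The June 2017 update, under Human subjects (Section V, item 3) and again in Section VI, A.2, reports that women randomised to active treatment in the first cohort had low progesterone levels. It then adds a second cohort: "We plan to enroll a minimum of 12 people with an imbalanced ratio of 6 active to 1 placebo". The second cohort's active product is also new: the team is "using a commercially available oral micronized progesterone rather than the previous medication that was compounded for the study". The update goes on to say that a final analysis might, if needed, set active women from the second cohort against placebo women from both.

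The Data Analysis text (Section V, item 12) still describes the single 1:1 trial. For Aim 1, "we will use generalized estimating equations (GEE), an autoregressive correlation structure a binomial distribution and either identity or log link", and "A time-by-treatment interaction will be included in the GEE model". The terms are therefore treatment, time and their interaction. Descriptive parameters are kept out of the primary model. Cohort is not mentioned there, nor among the urn randomisation variables, and the Aim 1 analysis set is not defined.

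**The concern.** Randomisation protects the comparison within each cohort. Once the allocation ratio changes, a pooled comparison that ignores cohort is no longer the randomised one, because the active arm draws a larger share of its women from cohort 2 than the placebo arm does. The cohorts differ in calendar time and possibly in recruitment mix and in what staff expect after the first cohort's levels became known. If any of these moves abstinence, some of that movement appears as a treatment effect.

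The protocol wants an effect size that can support a larger trial, so a shift in the estimate matters even where the type I error barely moves. A single treatment coefficient would also average two products that the protocol itself treats as different.

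**Working it through.** **The plan's own figure.** The plan gives no figure for pooled cohorts. Its only related number is power of 88% for 0.20 v 0.40 with 25 per arm, two-sided 0.05. A two-proportion test at one time point gives 33.5%, so the figure is not reproduced that way. That is a separate matter and nothing below depends on it.

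**Inputs from the documents.** Cohort 1: 25 active, 25 placebo as planned (the actual numbers are not given). Cohort 2: at least 12 at 6:1. Twelve is not a multiple of seven, so 10:2 and 11:1 are both shown. No maximum is stated, so 24:4 is shown as a larger case.

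**Assumption.** The cohort difference in abstinence is not given; 5 to 30 points is used.

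**Share of the cohort difference that leaks.** With no drug effect, on the risk-difference scale:

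bias = (cohort 2 share of active arm − cohort 2 share of placebo arm) × cohort difference

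- 10:2: 10/35 − 2/27 = 28.6% − 7.4% = 21%
- 11:1: 11/36 − 1/26 = 30.6% − 3.8% = 27%
- 24:4: 24/49 − 4/29 = 49.0% − 13.8% = 35%

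If cohort 1 had ended at 20:20, the first two would be 24% (10/30 − 2/22) and 31% (11/31 − 1/21).

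**Type I error.** Simulation at a single time point, with cohort 1 abstinence at 0.20 in both arms and cohort 2 higher in both arms. The unstratified z test is compared with the Cochran-Mantel-Haenszel test by cohort.

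| Cohort 2 split | Cohort difference | Bias, no cohort term | Two-sided type I error | Stratified: bias, error |
|---|---|---|---|---|
| 10:2 | 5 points | 1.1 | 4.8% | 0, 4.9% |
| 10:2 | 10 points | 2.1 | 4.9% | 0, 4.9% |
| 10:2 | 20 points | 4.2 | 5.7% | 0, 4.9% |
| 10:2 | 30 points | 6.3 | 7.1% | 0, 4.9% |
| 11:1 | 20 points | 5.3 | about 8% | 0, 4.8% |
| 24:4 | 20 points | 7.0 | 9.8% | 0, 4.9% |

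**Direction.** At 10:2 and 20 points, error in favour of progesterone is 4.8% against a nominal 2.5%. With the rates reversed (0.40 in cohort 1, 0.20 in cohort 2) the bias is −4.2 points, and only 0.95% of the 6.1% total error favours progesterone.

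**GEE check.** In an identity-link GEE on an enlarged copy of the 10:2 design with a 20-point cohort difference, adding a cohort term moved the treatment coefficient from 0.038 to −0.006. That shift of about 0.043 compares with 0.042 from the formula.

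**The optional comparison in the June 2017 update.** All active women come from cohort 2, so the leak is 1 − 2/27 = 93% (10:2) or 1 − 1/26 = 96% (11:1). A 20-point cohort difference at 10:2 gives 18.5 points of bias and 21.7% type I error.

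**What stratifying does not supply.** Mantel-Haenszel weights are 25×25/50 = 12.5 for cohort 1 and 10×2/12 = 1.67 for cohort 2, so cohort 2 carries 1.67/14.17 = 12%. If only the new product works and adds 20 points, the stratified estimate is 0.12 × 20 ≈ 2.4 points. The unstratified estimate is (25×0.20 + 10×0.40)/35 − 0.20 = 5.7 points.

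**The case against.** The strongest objection is that no text commits Aim 1 to an analysis of every woman in both cohorts. The phrase about all randomised subjects governs descriptive statistics, and the one about the full randomised sample concerns follow-up. The only pooled set named leaves out the first cohort's active arm. This stands. CONSORT is invoked, so an as-randomised analysis is a fair inference, but it is not stated. The point therefore applies to any analysis that pools the cohorts as randomised, and the undefined analysis set is part of the defect.

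The second objection is size. A reader might infer that the whole cohort difference becomes a false treatment effect, or that the error rate is seriously inflated in favour of progesterone. The documents do not support either for the as-randomised set. At the stated minimum about a fifth to a quarter leaks in. Two-sided error stays near nominal at 5 to 10 points, and the direction depends on which cohort abstains more, which is not given. The 24:4 case needs 28 women where the protocol states a minimum of 12 and pleads lack of funds.

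The third objection is that a cohort term works against learning about the new product, since it takes the estimate from 5.7 to 2.4 points when only that product works. It also leaves only about 10 v 2 women informing the optional comparison. Both are true and limit what the fix can deliver. They do not justify leaving the term out: within-cohort comparisons are the only randomised ones.

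**Conclusion.** The concern holds in conditional form. The change of ratio, the new product, the missing cohort term and the undefined analysis set are all on the page. The leak for as-randomised pooling is arithmetic: 21% of the cohort difference at 10:2 and 27% at 11:1, more if cohort 2 grows. At the planned minimum this is a modest bias, 1 to 6 points over the assumed 5 to 30 point range. It rests on 25:25 in cohort 1 and on a single time point for the error rates. The larger exposure is in the comparison the protocol does name, where nearly all of any cohort difference passes through. Because the correction is almost free, it should be made.

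**What to change.** In the Data Analysis text of Section V, item 12:

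1. State which cohorts and arms enter the Aim 1 analysis.
2. Include cohort as a fixed stratum in any as-randomised model that pools both cohorts. If the binomial model does not converge, use a cohort-stratified Mantel-Haenszel risk difference.
3. Report the arm difference within each cohort beside the pooled estimate. State that the pooled figure averages two products and gives cohort 2 only about 12% of the weight (at 10:2), so it says little about the new one.
4. Label the comparison of cohort 2 active women with placebo women from both cohorts as exploratory and non-randomised. Say that adjusting it for cohort leaves about 10 v 2 women, with a standard deviation of the difference of 0.31 to 0.38 (abstinence 0.20 to 0.40).

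The cost is one model term and some wording. At 10:2 with a 20-point cohort difference, the standard deviation of the estimate rises from 0.107 to 0.109. Power at 0.40 v 0.20 falls from about 38.5% to 37.3% if both products work equally and the cohorts do not otherwise differ.
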